15.3. Appendix 3: Assessment Windows

15.3.1. Definitions of Assessment Windows for Analyses

Laboratory data, vital signs, ECGs, health outcomes assessments, and genotypic/phenotypic data will be assigned to assessment windows according to actual dates rather than the nominal visit labels as recorded on the eCRF or in the laboratory database.

In most cases the window around an assessment will include all dates from the midpoints between the target day and that of the previous and the proceeding visits. In general, the nominal target study day for week w is $(7*w)+1$.

For parameters which are not scheduled to be assessed at particular visits, the all-inclusive assessment windows will still be used; however, data summaries will only report scheduled visits. Assessments at unscheduled visits will be included for ‘any time On-treatment’ time points and in data listings, as well any algorithms that make use of additional data (e.g., Snapshot).

Prior to visit slotting, assessments are first assigned to a study phase (screening, maintenance, extension, or long-term follow-up) based on the Tables in Section 15.4.1 and treatment state based on Section 15.4.2.

Maintenance phase assessments other than health outcome and PK are assigned based on the Study Day as shown in Table 8 and Table 10. Table 8 also includes visiting slotting for screening assessments. The analysis visits from Week 4 to Week 100 should be only applied to the assessments that are already assigned to Maintenance phase (on-treatment). Extension phase assessments other than health outcome and PK are assigned based on the Study Day as shown in Table 9. The analysis visits from Week 104 (except for Follow-up) in the Extension phase should be only applied to the assessments that are already assigned to Extension phase (on-treatment).

Long-term Follow-up phase assessments are assigned based on the LTFU study day as shown in

Table 11. The analysis visits in LTFU should be only applied to the assessments that are already assigned to LTFU phase regardless of treatment state. See Section 15.6.1, for derivation of Study Day and LTFU Study Day.

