15.4. Appendix 4: Study Phases and Treatment State

15.4.1. Study Phases

Assessments and events will be classified according to the time of occurrence relative to the Treatment Start Date defined in Section 15.6.1.

AEs will be assigned to study phases as defined in Table 13. For example, adverse events on/after start of maintenance phase IP and prior to start of Extension phase IP/LTFU ART will be assigned to the Maintenance Phase.

Laboratory data (efficacy, safety, PK and virology), HIV associated Conditions, health outcomes assessments, vital signs, and ECGs will be assigned to study phases as defined as in Table 14. For example, assessments/events occurring after start of maintenance phase IP and up to and including start of extension phase IP/LTFU ART will be assigned to the Maintenance Phase.

Assessments/events are assigned to study phases sequentially, starting from the top of each table. No study phases will be assigned to medications.

Table 13 Assignment of Study Phases for AEs

Study Phase	Definition
Screening	Date < Maintenance Treatment Start Date
Maintenance	
For participants continuing into Extension Phase: Maintenance Treatment Start Date ≤ Date < Date of Nominal Week 100 Visit
 
For participants not continuing into Extension Phase^[a]: Maintenance Treatment Start Date ≤ Date < LTFU ART Start Date For AEs leading to withdrawal and started on the same date as LTFU ART Start Date, Maintenance Phase, instead of Long-term Follow-up phase, will be assigned.

Extension	
Participants continuing into Extension Phase^[a]: Date of Nominal Week 100 Visit ≤ Date < LTFU ART Start Date For AEs leading to withdrawal and started on the same date as LTFU ART Start Date, Extension Phase, instead of Long-term Follow-up phase, will be assigned.

NOTES:

- Date = AE Start date
- [a] If participants have missing LTFU ART start date, only the lower bound will be considered in the derivation.

Table 14 Assignment of Study Phases for Lab Assessments (including PK and Virology), ECG, Protocol Deviations, Vital Sign, Health Outcomes, HIV Associated Conditions

Study Phase	Definition
Screening	Date \leq Maintenance Treatment Start Date Note: 2-hour post-dose ECG taken on the Maintenance Treatment Start Date will be excluded.

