Maintenance	For participants continuing into Extension Phase: Maintenance Treatment Start Date < Date \leq Date of Nominal Week 100 Visit Note: 2-hour post-dose ECG taken on the Maintenance Treatment Start Date will be included. For participants not continuing into Extension Phase^[a]: Maintenance Treatment Start Date < Date \leq LTFU ART Start Date Note: 2-hour post-dose ECG taken on the Maintenance Treatment Start Date will be included.
Extension	Participants continuing into Extension Phase^[a]: Date of Nominal Week 100 Visit < Date \leq LTFU ART Start Date

- Date = start or assessment date
- [a] If participants have missing LTFU ART start date (i.e. the participants have not started ART in LTFU yet), only the lower bound of the window will be considered in the derivation.

Table 15 Assignment to Long-term Follow-up Phase

Study Phase	Definition
Long-term Follow-up	Date > max (Last IM Injection Date, Last Oral Bridging End Date)

- Date = Assessment/Start Date
- For AEs leading to withdrawal and started on the same date as LTFU ART Start Date, maintenance phase or extension phase depending on participant's continuation status to extension phase, instead of long-term follow-up phase, will be assigned. Refer to [Table 13](#) for details.

Only participants who received at least one CAB and/or RPV injection will enter the long-term follow-up. Note that the long-term follow-up phase and maintenance/extension phases are not necessarily mutually exclusive and are to be defined with separate phase variables in the datasets. For example, an Q4W IM participant who has Week 44 injection and withdrawal at Week 48 without receiving Week 48 injection, the “Week 48 withdrawal visit” belongs to both the maintenance phase and long-term follow-up phase.

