15.4.2. Treatment State

Within each treatment study phase (i.e. Maintenance and Extension—based on assignment of study phase described in Section [15.4.1](#)), only those assessments which occur within the ranges shown in [Table 16](#) will be considered ‘on-treatment’ for the given phase. No treatment states will be assigned to medications.

Table 16 Treatment State within Study Phases^b

Study Phase ^a	Treatment State	Date Range
Screening	Pre-treatment	All assessments/events within the phase
Maintenance	On-treatment	Q8W arm: Date ≤ max (Date of Last Injection + 63, Date of Last Dose of Oral CAB+RPV + 1)
		Q4W arm: Date ≤ max (Date of Last Injection + 35, Date of Last Dose of Oral CAB+RPV + 1)
	Post-treatment	Q8W arm: Date > max (Date of Last Injection + 63, Date of Last Dose of Oral CAB+RPV + 1)
		Q4W arm: Date > max (Date of Last Injection + 35, Date of Last Dose of Oral CAB+RPV + 1)
Extension	On-treatment	Q8W arm: Date ≤ max (Date of Last Injection + 63, Date of Last Dose of Oral CAB+RPV + 1)
		Q4W arm: Date ≤ max (Date of Last Injection + 35, Date of Last Dose of Oral CAB+RPV + 1)
	Post-treatment	Q8W arm: Date > max (Date of Last Injection + 63, Date of Last Dose of Oral CAB+RPV + 1)
		Q4W arm: Date > max (Date of Last Injection + 35, Date of Last Dose of Oral CAB+RPV + 1)
Long-term Follow-up	On-treatment	Q8W arm: Date ≤ min (LTFU ART start date, max (Date of Last Injection + 63, Date of Last Dose of Oral CAB+RPV + 1))
		Q4W arm: Date ≤ min (LTFU ART start date, max (Date of Last Injection + 35, Date of Last Dose of Oral CAB+RPV + 1))
	Post-treatment	Q8W arm: Date > min (LTFU ART start date, max (Date of Last Injection + 63, Date of Last Dose of Oral CAB+RPV + 1))
		Q4W: Date > min (LTFU ART start date, max (Date of Last Injection + 35, Date of Last Dose of Oral CAB+RPV + 1))
NOTE:		

 • Date = Assessment/Start Date. a. Treatment State is determined after data has been assigned to the study phases as defined in Section 15.4.1. b. Last injection and/or last dose of oral CAB+RPV are only applied to participants who permanently discontinued the study treatment. The assessments for participants who did not permanently discontinue the study treatment will be considered 'On-treatment'. For participants continuing into extension phase, all data assigned to maintenance phase per Section 15.4.1 will be considered 'On-treatment'. 		

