15.10. Appendix 10: Variables Defined for Time to Event Analysis

Programming Instructions for the Kaplan-Meier analysis of treatment-related discontinuation equals failure (TRDF)		
Condition	Censor Status	Event Description/AVAL
1. Participant met CVF event criteria during the Maintenance Phase (based on derived CVF)	CNSR=0	EVNTDESC=CVF AVAL=Study Day of SVF* *immediately preceding CVF
2. Participant with Maintenance Phase withdrawal due to ' Lack of Efficacy ', ' Treatment Related AE ', ' Intolerability due to Injection ', or ' Protocol Defined Safety Stopping Criteria ' during Maintenance Phase Note: primary reason and/or standardized subreason for discontinuation based on Maintenance Conclusion form in the eCRF. ' Protocol Defined Safety Stopping Criteria ' includes GSK defined liver chemistry stopping criteria, renal toxicity criteria and QTc withdrawal criteria. Treatment Related AE' is defined as participants who have primary reason for withdrawal =AE and who have at least one AE considered drug related and leading to withdrawal/permanent discontinuation of investigational product.	CNSR=0	EVNTDESC= terms in italic, respectively. For Q4W arm: AVAL= min [Study Day of Maintenance Phase Discontinuation, max(Study Day of Last Injection + 35, Study Day of Last Dose of Oral CAB+RPV + 1)] For Q8W arm: AVAL= min [Study Day of Maintenance Phase Discontinuation, max(Study Day of Last Injection + 63, Study Day of Last Dose of Oral CAB/RPV + 1)] Note: Date of Maintenance Phase discontinuation is from the Maintenance Phase Conclusion form in the eCRF.
If none of the above conditions met		
3. Participant with Maintenance Phase withdrawal due to other reasons	CNSR=1	EVNTDESC='Censored due to Study Discontinuation for Other Reasons' AVAL will be defined as the same as above 2
4. Participant who did not have premature withdrawal from	CNSR=1	EVNTDESC='Censored due to data cutoff for analysis'

Programming Instructions for the Kaplan-Meier analysis of treatment-related discontinuation equals failure (TRDF)		
Condition	Censor Status	Event Description/AVAL

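### In the exploratory TRDF/ERDF Kaplan-Meier analysis, a virologic failure that starts after study drug has ended still counts as an event, while other withdrawals are censored by the end of on-treatment time

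*SAP*

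**What the plan says.** Appendix 10 applies its conditions in order.

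- **Condition 1 (event).** "Participant met CVF event criteria during the Maintenance Phase (based on derived CVF"), with time set by "AVAL=Study Day of SVF". No treatment state is named and the time is not capped.
- **Condition 2 (event).** Withdrawal for a listed reason: lack of efficacy, treatment-related AE, injection intolerability or a safety stopping criterion for TRDF; lack of efficacy only for ERDF. For Q4W the time is "min [Study Day of Maintenance Phase Discontinuation, max(Study Day of Last Injection + 35, Study Day of Last Dose of Oral CAB+RPV + 1")]. Q8W uses 63 days in place of 35.
- **Condition 3 (censored).** Withdrawal for any other reason; "AVAL will be defined as the same as above 2".

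The length of the Maintenance Phase is set in Section 15.4.1. Laboratory assessments "up to and including start of extension phase IP/LTFU ART will be assigned to the Maintenance Phase". If the follow-up ART date is missing, the note to Table 14 says that "only the lower bound of the window will be considered in the derivation". Table 16 (Section 15.4.2) then divides the phase by treatment state. Its post-treatment part for Q4W is "Q4W arm: Date > max (Date of Last Injection + 35, Date of Last Dose of Oral CAB+RPV + 1"), and for Q8W the same with 63 days.

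**The concern.** Tables 14 and 16 together create viral loads that lie in the Maintenance Phase but are post-treatment. Condition 1 admits them. Conditions 2 and 3 end no later than the on-treatment limit.

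Two participants who withdraw on the same day for the same reason are then followed for different lengths of time, and what decides the length is whether virus later rebounds off drug. Kaplan-Meier estimation needs time at risk to be fixed without reference to the later outcome. Here the rebound enters as an event, but the corresponding event-free time off drug of other withdrawals is not counted.

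At stake is the meaning of TRDF and ERDF as measures of failure on the randomized regimens. Few CVFs per arm are to be expected, so one or two such cases could shift the arm comparison. The limits of 35 and 63 days also differ by arm, so the arms may not be affected equally.

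**Working it through.** The SAP gives no CVF rate or Kaplan-Meier estimate, so there is no planned figure to reproduce. The check is a worked case followed by a sizing over assumed ranges.

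**Worked case (invented dates, SAP rules).** Last injection Day 169, no later oral dosing, withdrawal for a reason outside Condition 2 on Day 205, follow-up ART from Day 260, HIV-1 RNA at or above 200 c/mL on Days 238 and 245.

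| Step | Q4W | Q8W |
|---|---|---|
| End of on-treatment time (Table 16) | 169 + 35 = Day 204 | 169 + 63 = Day 232 |
| Phase of Days 238 and 245 (Table 14; both ≤ 260) | Maintenance | Maintenance |
| Treatment state of Days 238 and 245 | Post-treatment | Post-treatment |
| Condition 1 as written | Event, Day 238 | Event, Day 238 |
| Condition 3 if there were no rebound | min(205, 204) = censored Day 204 | min(205, 232) = censored Day 205 |

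The same person is at risk for 34 days longer (Q4W) or 33 days longer (Q8W) only because an event followed.

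**Size per case.** Input from SAP Section 1: 510 participants per arm. An event at a time when survival is S and R participants are at risk lowers the curve by S/R. With S = 1 and R = 510 this is 1/510 = 0.196 percentage points. Earlier events and censoring change it little. Kaplan-Meier failure at Day 364 was simulated with 200 data sets per setting, moving k otherwise censored withdrawals to events 10 to 59 days after their censoring day:

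| Assumed on-treatment events / censored withdrawals | Failure, k = 0 | Added, k = 1 | k = 2 | k = 3 | k = 5 |
|---|---|---|---|---|---|
| 5 / 25 | 1.01% | 0.20 | 0.40 | 0.60 | 1.00 |
| 10 / 40 | 2.05% | 0.20 | 0.41 | 0.61 | 1.01 |
| 20 / 60 | 4.22% | 0.21 | 0.41 | 0.62 | 1.03 |

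(Additions in percentage points.) In a separate simulation with 6% other withdrawals, the Greenwood standard error was 0.45 points at 1% CVF and 0.64 points at 2%. One case is therefore a little under half, or about a third, of a standard error.

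**The direction can reverse.** Suppose the last injection is on Day 309, withdrawal for a treatment-related AE on Day 340, and suspected failure on Day 400, confirmed before ART. On-treatment time ends on Day 344 (Q4W) or Day 372 (Q8W), so Day 400 is post-treatment in both arms. Condition 2 would give a TRDF event at min(340, 344) or min(340, 372), which is Day 340 either way. Condition 1 comes first and moves it to Day 400, past Week 48. That lowers the Week 48 TRDF failure estimate.

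**The case against.** Several stronger readings are tempting, and the SAP does not support them.

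- **That the by-visit CVF table is restricted to on-treatment visits and so contradicts the Kaplan-Meier analysis.** A reader might infer this from Section 15.3.1: "The analysis visits from Week 4 to Week 100 should be only applied to the assessments that are already assigned to Maintenance phase (on-treatment"). That is a general visit-slotting rule. Table 2.23 is itself titled for the Maintenance Phase, Section 15.3.6 makes all applicable valid assessments available for CVF identification, and the Week 24 notes name the non-snapshot window for the by-visit and the Kaplan-Meier tables alike. No text expressly limits CVF in the by-visit table.
- **That a secondary endpoint is biased.** The proportion with CVF is secondary (Section 7.2.1). TRDF and ERDF are listed as exploratory in Table 3, and as composites they differ from the CVF proportion by design.
- **That failure is overstated as a matter of fact.** This needs participants whose suspected failure is post-treatment, confirmed before ART, and who would otherwise be censored. Section 2.3 has participants who discontinue after an injection start HAART, and the scheduled follow-up visits are at months 3, 6, 9 and 12, so such cases may be few or absent.

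Two further objections carry weight. Section 15.6.3 leaves the CVF definition to protocol Section 5.5.4, which was not available here; if it already requires on-treatment samples, the change only makes that explicit. And these are long-acting injections, so counting failure after the dosing window is a choice that could be defended. But that choice would call for follow-up over the same extended period for every withdrawal, and Condition 3 does not provide it. The mismatch between Conditions 1 and 3 remains.

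**Conclusion.** The point holds, narrowly. As written, Condition 1 lets post-treatment rebound count as an event in TRDF and ERDF, later than the day on which the same participant would otherwise have been censored. The flaw lies in the rule itself and does not depend on how many cases arise.

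Its effect does depend on that number: about 0.2 percentage points per affected, otherwise censored participant in an arm of 510, about 0.6 for three, and nothing if there are none. The count is not in the SAP, and the event and withdrawal numbers used for sizing are assumptions. For participants who fail under Condition 2 the effect can run the other way. The conclusion assumes that the protocol's CVF definition does not already impose an on-treatment limit.

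The primary analysis is not touched, because the Snapshot windows (Table 10) apply only to on-treatment viral loads.

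**What to change.** In Condition 1 of Appendix 10, require the suspected-failure viral load to be on-treatment per Table 16, and allow the confirming value to come later. Classify a participant whose suspected failure is post-treatment under Condition 2 or 3 according to the reason for withdrawal. List post-treatment rebounds separately. The same wording carries over to ERDF.

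Leave the protocol-defined CVF count (Table 2.24) and the CVF population unchanged; nothing in the SAP alone justifies redefining them.

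A small gap remains where discontinuation precedes the Table 16 limit (Days 206 to 232 for Q8W in the worked case). Events there fall within the on-treatment window, and counting them is reasonable.

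The cost is one sentence and one derivation flag. Off-drug rebounds no longer count in TRDF/ERDF, so the reported failure estimate may fall slightly; the separate listing keeps them visible.

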15.11. Appendix 11: Identification of Adverse Events of Special Interest

The adverse events of special interest are identified based on MedDRA coded values and/or AE data available in the study database. The system organ classes (SOCs), preferred terms (PTs) or codes, Standardised MedDRA Queries (SMQs), High Level Group Terms (HLGTs), and High Level Terms (HLT) below are from MedDRA 21.1. SMQs use narrow terms unless otherwise specified. In case there is a change to the version of MedDRA at time of reporting, the coded values based on the MedDRA version at the time of reporting will be used. The additional events may also be added based on the blinded review of AE data collected on study prior to the database freeze.

1. Hepatic Safety Profile: Assessment of risk of hepatotoxicity

Hepatic failure, fibrosis and cirrhosis and other liver damage-related conditions (SMQ)

PT	PT Code
Acquired hepatocerebral degeneration	10080860
Acute hepatic failure	10000804
Acute on chronic liver failure	10077305
Acute yellow liver atrophy	10070815
Ascites	10003445
Asterixis	10003547
Bacterascites	10068547
Biliary cirrhosis	10004659
Biliary fibrosis	10004664
Cholestatic liver injury	10067969
Chronic hepatic failure	10057573
Coma hepatic	10010075
Cryptogenic cirrhosis	10063075
Diabetic hepatopathy	10071265
Drug-induced liver injury	10072268
Duodenal varices	10051010
Gallbladder varices	10072319
Gastric variceal injection	10076237
Gastric variceal ligation	10076238
Gastric varices	10051012
Gastric varices haemorrhage	10057572
Hepatectomy	10061997
Hepatic atrophy	10019637
Hepatic calcification	10065274
Hepatic cirrhosis	10019641
Hepatic encephalopathy	10019660
Hepatic encephalopathy prophylaxis	10066599

PT	PT Code
Hepatic failure	10019663
Hepatic fibrosis	10019668
Hepatic hydrothorax	10067365
Hepatic infiltration eosinophilic	10064668
Hepatic lesion	10061998
Hepatic necrosis	10019692
Hepatic steato-fibrosis	10077215
Hepatic steatosis	10019708
Hepatitis fulminant	10019772
Hepatobiliary disease	10062000
Hepatocellular foamy cell syndrome	10053244
Hepatocellular injury	10019837
Hepatopulmonary syndrome	10052274
Hepatorenal failure	10019845
Hepatorenal syndrome	10019846
Hepatotoxicity	10019851
Intestinal varices	10071502
Intestinal varices haemorrhage	10078058
Liver and small intestine transplant	10052280
Liver dialysis	10076640
Liver disorder	10024670
Liver injury	10067125
Liver operation	10062040
Liver transplant	10024714
Lupoid hepatic cirrhosis	10025129
Minimal hepatic encephalopathy	10076204
Mixed liver injury	10066758
Nodular regenerative hyperplasia	10051081
Non-alcoholic fatty liver	10029530
Non-alcoholic steatohepatitis	10053219
Non-cirrhotic portal hypertension	10077259
Oedema due to hepatic disease	10049631
Oesophageal varices haemorrhage	10030210
Peripancreatic varices	10073215
Portal fibrosis	10074726
Portal hypertension	10036200
Portal hypertensive colopathy	10079446
Portal hypertensive enteropathy	10068923
Portal hypertensive gastropathy	10050897

PT	PT Code
Portal vein cavernous transformation	10073979
Portal vein dilatation	10073209
Portopulmonary hypertension	10067281
Primary biliary cholangitis	10080429
Regenerative siderotic hepatic nodule	10080679
Renal and liver transplant	10052279
Retrograde portal vein flow	10067338
Reye's syndrome	10039012
Reynold's syndrome	10070953
Splenic varices	10067823
Splenic varices haemorrhage	10068662
Steatohepatitis	10076331
Subacute hepatic failure	10056956
Varices oesophageal	10056091
Varicose veins of abdominal wall	10072284
White nipple sign	10078438

Hepatitis, non-infectious (SMQ)

PT	PT Code
Acute graft versus host disease in liver	10066263
Allergic hepatitis	10071198
Alloimmune hepatitis	10080576
Autoimmune hepatitis	10003827
Chronic graft versus host disease in liver	10072160
Chronic hepatitis	10008909
Graft versus host disease in liver	10064676
Hepatitis	10019717
Hepatitis acute	10019727
Hepatitis cholestatic	10019754
Hepatitis chronic active	10019755
Hepatitis chronic persistent	10019759
Hepatitis fulminant	10019772
Hepatitis toxic	10019795
Immune-mediated hepatitis	10078962
Ischaemic hepatitis	10023025
Lupus hepatitis	10067737
Non-alcoholic steatohepatitis	10053219
Radiation hepatitis	10051015
Steatohepatitis	10076331

2. Hypersensitivity Reactions (HSR)

Drug reaction with eosinophilia and systemic symptoms syndrome (SMQ)

PT	PT Code
Drug reaction with eosinophilia and systemic symptoms	10073508
Pseudolymphoma	10037127

PTs (Selective)

PT	PT Code
Drug hypersensitivity	10013700
Hypersensitivity	10020751
Type IV Hypersensitivity reaction	10053613
Eosinophilia	10014950
Eye swelling	10015967
Eyelid oedema	10015993
Lip swelling	10024570
Angioedema	10002424
Circumoral oedema	10052250
Face oedema	10016029
Idiopathic angioedema	10073257
Lip oedema	10024558
Mouth swelling	10075203
Oedema mouth	10030110
Periorbital oedema	10034545
Swelling face	10042682
Periorbital swelling	10056647
Swelling of eyelid	10042690

3. Rash

Severe cutaneous adverse reactions (SMQ)

PT	PT Code
Acute generalised exanthematous pustulosis	10048799
Cutaneous vasculitis	10011686
Dermatitis bullous	10012441
Dermatitis exfoliative	10012455
Dermatitis exfoliative generalised	10012456
Drug reaction with eosinophilia and systemic symptoms	10073508

PT	PT Code
Epidermal necrosis	10059284
Erythema multiforme	10015218
Exfoliative rash	10064579
Oculomucocutaneous syndrome	10030081
Skin necrosis	10040893
Stevens-Johnson syndrome	10042033
Toxic epidermal necrolysis	10044223
Toxic skin eruption	10057970

PTs (Selective), Grade 3 and higher

PT	PT Code
Eyelid rash	10074620
Genital rash	10018175
Mucocutaneous rash	10056671
Nodular rash	10075807
Perineal rash	10075364
Rash	10037844
Rash erythematous	10037855
Rash generalised	10037858
Rash macular	10037867
Rash maculo-papular	10037868
Rash maculovesicular	10050004
Rash morbilliform	10037870
Rash papular	10037876
Rash rubelliform	10057984
Rash scarlatiniform	10037890
Rash vesicular	10037898
Rash pruritic	10037884
Rash follicular	10037857
Rash pustular	10037888
Drug eruption	10013687

4. Prolongation of the Corrected QT Interval of the ECG in Supratherapeutic Doses

Torsade de pointes/QT prolongation (SMQ)

PT	PT Code
Electrocardiogram QT interval abnormal	10063748

PT	PT Code
Electrocardiogram QT prolonged	10014387
Long QT syndrome	10024803
Long QT syndrome congenital	10057926
Torsade de pointes	10044066
Ventricular tachycardia	10047302

PTs (Selective)

PT	PT Code
Electrocardiogram repolarisation abnormality	10052464

5. Suicidal Ideation/Behaviour**Suicide/self-injury (SMQ)**

PT	PT Code
Assisted suicide	10079105
Columbia suicide severity rating scale abnormal	10075616
Completed suicide	10010144
Depression suicidal	10012397
Intentional overdose	10022523
Intentional self-injury	10022524
Poisoning deliberate	10036000
Self-injurious ideation	10051154
Suicidal behaviour	10065604
Suicidal ideation	10042458
Suicide attempt	10042464
Suicide threat	10077417
Suspected suicide attempt	10081704

6. Depression**Depression (excl suicide and self injury) (SMQ)**

PT	PT Code
Activation syndrome	10066817
Adjustment disorder with depressed mood	10001297
Adjustment disorder with mixed anxiety and depressed mood	10001299
Agitated depression	10001496
Anhedonia	10002511

PT	PT Code
Antidepressant therapy	10054976
Childhood depression	10068631
Decreased interest	10011971
Depressed mood	10012374
Depression	10012378
Depression postoperative	10012390
Depressive symptom	10054089
Dysphoria	10013954
Electroconvulsive therapy	10014404
Feeling guilty	10049708
Feeling of despair	10016344
Feelings of worthlessness	10016374
Helplessness	10077169
Major depression	10057840
Menopausal depression	10067371
Mixed anxiety and depressive disorder	10080836
Perinatal depression	10078366
Persistent depressive disorder	10077804
Post stroke depression	10070606
Postictal depression	10071324

7. Bipolar Disorder

HLGT Manic and Bipolar mood disorders and disturbances

PT	PT Code
Bipolar I disorder	10004939
Bipolar II disorder	10004940
Bipolar disorder	10057667
Cyclothymic disorder	10011724
Hypomania	10021030
Mania	10026749

8. Psychosis

Psychosis and psychotic disorders (SMQ)

PT	PT Code
Acute psychosis	10001022
Alcoholic psychosis	10001632

PT	PT Code
Alice in wonderland syndrome	10001666
Brief psychotic disorder with marked stressors	10048549
Brief psychotic disorder without marked stressors	10056395
Brief psychotic disorder, with postpartum onset	10006362
Charles Bonnet syndrome	10063354
Childhood psychosis	10061040
Clang associations	10009232
Cotard's syndrome	10059591
Delusion	10012239
Delusion of grandeur	10012241
Delusion of reference	10012244
Delusion of replacement	10012245
Delusional disorder, erotomanic type	10012249
Delusional disorder, grandiose type	10012250
Delusional disorder, jealous type	10012251
Delusional disorder, mixed type	10012252
Delusional disorder, persecutory type	10053195
Delusional disorder, somatic type	10012254
Delusional disorder, unspecified type	10012255
Delusional perception	10012258
Dementia of the Alzheimer's type, with delusions	10012295
Depressive delusion	10063033
Derailment	10012411
Epileptic psychosis	10059232
Erotomanic delusion	10015134
Flight of ideas	10016777
Hallucination	10019063
Hallucination, auditory	10019070
Hallucination, gustatory	10019071
Hallucination, olfactory	10019072
Hallucination, synaesthetic	10062824
Hallucination, tactile	10019074
Hallucination, visual	10019075
Hallucinations, mixed	10019079
Hypnagogic hallucination	10020927
Hypnopompic hallucination	10020928
Hysterical psychosis	10062645
Ideas of reference	10021212
Illusion	10021403

PT	PT Code
Jealous delusion	10023164
Loose associations	10024825
Mixed delusion	10076429
Neologism	10028916
Neuroleptic-induced deficit syndrome	10075295
Paranoia	10033864
Paranoid personality disorder	10033869
Parkinson's disease psychosis	10074835
Paroxysmal perceptual alteration	10063117
Persecutory delusion	10034702
Postictal psychosis	10070669
Post-injection delirium sedation syndrome	10072851
Posturing	10036437
Psychosis postoperative	10065617
Psychotic behaviour	10037249
Psychotic disorder	10061920
Psychotic disorder due to a general medical condition	10061921
Reactive psychosis	10053632
Rebound psychosis	10074833
Schizoaffective disorder	10039621
Schizoaffective disorder bipolar type	10068889
Schizoaffective disorder depressive type	10068890
Schizophrenia	10039626
Schizophreniform disorder	10039647
Schizotypal personality disorder	10039651
Senile psychosis	10039987
Shared psychotic disorder	10040535
Somatic delusion	10041317
Somatic hallucination	10062684
Substance-induced psychotic disorder	10072388
Tangentiality	10043114
Thought blocking	10043495
Thought broadcasting	10052214
Thought insertion	10043496
Thought withdrawal	10043497
Transient psychosis	10056326
Waxy flexibility	10047853

9. Mood Disorders

HLGT Mood disorders and disturbances NEC, Psychiatric disorders SOC

PT	PT Code
Crying	10011469
Mood swings	10027951
Boredom	10048909
Mood altered	10027940
Apathy	10002942
Affective ambivalence	10077173
Emotional poverty	10014557
Euphoric mood	10015535
Premenstrual dysphoric disorder	10051537
Alexithymia	10077719
Laziness	10051602
Blunted affect	10005885
Constricted affect	10010778
Affect lability	10054196
Anger	10002368
Affective disorder	10001443
Lethargy	10024264
Listless	10024642
Inappropriate affect	10021588
Dysphoria	10013954
Mood disorder due to a general medical condition	10027944
Morose	10027977
Screaming	10039740
Steroid withdrawal syndrome	10042028
Emotional disorder	10014551
Irritability	10022998
Moaning	10027783
Premenstrual syndrome	10036618
Neuroleptic-induced deficit syndrome	10075295
Substance-induced mood disorder	10072387
Flat affect	10016759
Diencephalic syndrome of infancy	10012774
Emotional distress	10049119
Frustration tolerance decreased	10077753
Seasonal affective disorder	10039775

10. Anxiety**HLGT Anxiety disorders and symptoms**

PT	PT Code
Acrophobia	1000605
Activation syndrome	10066817
Acute stress disorder	10001084
Aerophobia	10080300
Agitation	10001497
Agitation neonatal	10001500
Agitation postoperative	10049989
Agoraphobia	10001502
Akathisia	10001540
Algophobia	10078056
Animal phobia	10002518
Anniversary reaction	10074066
Anticipatory anxiety	10002758
Anxiety	10002855
Anxiety disorder	10057666
Anxiety disorder due to a general medical condition	10002859
Arachnophobia	10051408
Astraphobia	10078372
Autophobia	10071070
Body dysmorphic disorder	10052793
Burnout syndrome	10065369
Claustrophobia	10009244
Compulsions	10010219
Compulsive cheek biting	10076510
Compulsive handwashing	10071263
Compulsive hoarding	10068007
Compulsive lip biting	10066241
Compulsive shopping	10067948
Dermatillomania	10065701
Dysmorphophobia	10049096
Emetophobia	10070637
Fear	10016275
Fear of animals	10016276
Fear of closed spaces	10016277
Fear of crowded places	10050365
Fear of death	10066392

PT	PT Code
Fear of disease	10016278
Fear of eating	10050366
Fear of falling	10048744
Fear of injection	10073753
Fear of open spaces	10016279
Fear of pregnancy	10067035
Fear of weight gain	10016280
Fear-related avoidance of activities	10080136
Generalised anxiety disorder	10018075
Glossophobia	10080077
Haemophobia	10073458
Haphephobia	10067580
Hydrophobia	10053317
Hyperarousal	10080831
Immunisation anxiety related reaction	10075205
Kinesiophobia	10078430
Limited symptom panic attack	10024511
Mysophobia	10078769
Nail picking	10066779
Nervousness	10029216
Neurosis	10029333
Noctiphobia	10057946
Nocturnal fear	10057948
Nosophobia	10063546
Obsessive need for symmetry	10077179
Obsessive rumination	10056264
Obsessive thoughts	10029897
Obsessive-compulsive disorder	10029898
Obsessive-compulsive symptom	10077894
Ochlophobia	10050095
Osmophobia	10060765
Paediatric autoimmune neuropsychiatric disorders associated with streptococcal infection	10072147
Panic attack	10033664
Panic disorder	10033666
Panic reaction	10033670
Paruresis	10069024
Performance fear	10034432
Phagophobia	10050096
Pharmacophobia	10069423

PT	PT Code
Phobia	10034912
Phobia of driving	10056676
Phobia of exams	10034913
Phobic avoidance	10034918
Phonophobia	10054956
Photiaugiaphobia	10064420
Post-traumatic stress disorder	10036316
Postpartum neurosis	10036419
Postpartum stress disorder	10056394
Procedural anxiety	10075204
Pseudoangina	10056610
Selective mutism	10039917
Separation anxiety disorder	10040045
Sitophobia	10080170
Social anxiety disorder	10041242
Social fear	10041247
Stress	10042209
Tension	10043268
Terminal agitation	10077416
Thanatophobia	10064723
Thermophobia	10075147
Trichotemnomania	10072752
Trichotillomania	10044629

11. Sleep Disorders

HLGT Sleep Disorders and Disturbances

PT	PT Code
Behavioural insomnia of childhood	10072072
Hyposomnia	10067530
Initial insomnia	10022035
Insomnia	10022437
Middle insomnia	10027590
Terminal insomnia	10068932
Breathing-related sleep disorder	10006344
Dyssomnia	10061827
Hypersomnia	10020765
Periodic limb movement disorder	10064600
Pickwickian syndrome	10035004

PT	PT Code
Poor quality sleep	10062519
Sleep apnoea syndrome	10040979
Somnolence	10041349
Somnolence neonatal	10041350
Stupor	10042264
Upper airway resistance syndrome	10063968
Cataplexy	10007737
Hypnagogic hallucination	10020927
Hypnopompic hallucination	10020928
Narcolepsy	10028713
Sleep attacks	10040981
Sleep paralysis	10041002
Abnormal dreams	10000125
Abnormal sleep-related event	10061613
Confusional arousal	10067494
Exploding head syndrome	10080684
Loss of dreaming	10065085
Nightmare	10029412
Parasomnia	10061910
Rapid eye movement sleep behaviour disorder	10077299
Rapid eye movements sleep abnormal	10037841
Sleep inertia	10067493
Sleep sex	10067492
Sleep talking	10041009
Sleep terror	10041010
Sleep-related eating disorder	10067315
Somnambulism	10041347
Hypersomnia related to another mental condition	10020767
Hypersomnia-bulimia syndrome	10053712
Insomnia related to another mental condition	10022443
Sleep disorder	10040984
Sleep disorder due to a general medical condition	10063910
Sleep disorder due to general medical condition, hypersomnia type	10040985
Sleep disorder due to general medical condition, insomnia type	10040986
Sleep disorder due to general medical condition, mixed type	10040987
Sleep disorder due to general medical condition, parasomnia type	10040988
Sopor	10058709

PT	PT Code
Advanced sleep phase	10001423
Circadian rhythm sleep disorder	10009191
Delayed sleep phase	10012209
Irregular sleep phase	10022995
Irregular sleep wake rhythm disorder	10080301
Non-24-hour sleep-wake disorder	10078086
Shift work disorder	10078088

HLGT Sleep disturbances (incl subtypes)

PT	PT Code
Abnormal dreams	10000125
Abnormal sleep-related event	10061613
Confusional arousal	10067494
Loss of dreaming	10065085
Sleep inertia	10067493
Sleep paralysis	10041002
Sleep sex	10067492
Sleep talking	10041009
Sleep terror	10041010
Sleep-related eating disorder	10067315
Somnambulism	10041347
Behavioural insomnia of childhood	10072072
Hyposomnia	10067530
Initial insomnia	10022035
Insomnia	10022437
Middle insomnia	10027590
Terminal insomnia	10068932
Advanced sleep phase	10001423
Circadian rhythm sleep disorder	10009191
Delayed sleep phase	10012209
Irregular sleep phase	10022995
Irregular sleep wake rhythm disorder	10080301
Non-24-hour sleep-wake disorder	10078086
Shift work disorder	10078088
Cataplexy	10007737
Hypersomnia	10020765
Narcolepsy	10028713
Central-alveolar hypoventilation	10007982
Sleep apnoea syndrome	10040979

PT	PT Code
Breathing-related sleep disorder	10006344
Dyssomnia	10061827
Fatal familial insomnia	10072077
Microsleep	10076954
Periodic limb movement disorder	10064600
Pickwickian syndrome	10035004
Poor quality sleep	10062519
Rapid eye movement sleep behaviour disorder	10077299
Rapid eye movements sleep abnormal	10037841
Sleep deficit	10080881
Sudden onset of sleep	10050014
Upper airway resistance syndrome	10063968

12. Injection Site Reactions (ISR) from Study Drug Injections

Study drug ISR data available in the database, i.e. data collected from non-serious ISR AE eCRF form and collected serious adverse events with 'STUDY DRUG INJECTION SITE' included in the AE term.

13. Seizures and Seizure-like Events

Convulsions (SMQ)

PT	PT Code
2-Hydroxyglutaric aciduria	10078971
Acquired epileptic aphasia	10052075
Acute encephalitis with refractory, repetitive partial seizures	10076948
Alcoholic seizure	10056347
Aspartate-glutamate-transporter deficiency	10079140
Atonic seizures	10003628
Atypical benign partial epilepsy	10056699
Automatism epileptic	10003831
Autonomic seizure	10049612
Baltic myoclonic epilepsy	10054895
Benign familial neonatal convulsions	10067866
Benign rolandic epilepsy	10070530
Biotinidase deficiency	10071434
Change in seizure presentation	10075606
Clonic convulsion	10053398
Convulsion in childhood	10052391

PT	PT Code
Convulsion neonatal	10010911
Convulsions local	10010920
Convulsive threshold lowered	10010927
CSWS syndrome	10078827
Deja vu	10012177
Double cortex syndrome	10073490
Dreamy state	10013634
Drug withdrawal convulsions	10013752
Early infantile epileptic encephalopathy with burst-suppression	10071545
Eclampsia	10014129
Epilepsy	10015037
Epilepsy surgery	10079824
Epilepsy with myoclonic-atonic seizures	10081179
Epileptic aura	10015049
Epileptic psychosis	10059232
Febrile convulsion	10016284
Febrile infection-related epilepsy syndrome	10079438
Focal dyscognitive seizures	10079424
Frontal lobe epilepsy	10049424
Generalised non-convulsive epilepsy	10018090
Generalised tonic-clonic seizure	10018100
Glucose transporter type 1 deficiency syndrome	10078727
Gray matter heterotopia	10080533
Hemimegalencephaly	10078100
Hyperglycaemic seizure	10071394
Hypocalcaemic seizure	10072456
Hypoglycaemic seizure	10048803
Hyponatraemic seizure	10073183
Idiopathic generalised epilepsy	10071081
Infantile spasms	10021750
Juvenile myoclonic epilepsy	10071082
Lafora's myoclonic epilepsy	10054030
Lennox-Gastaut syndrome	10048816
Migraine-triggered seizure	10076676
